### 16.3 Appendix 3: Specific Renal Alert Criteria and Actions and Event Follow-up

**Table 16-4 Specific Renal Alert Criteria and Actions**

Renal Event	Actions
Confirmed sCR increase 25 – 49%	
 
Consider causes and possible interventions
 
follow-up within 2-5 days
 

sCR increase a 50 % + OR if <18 years old, eGFR 35 mL/min/1.73 m^2	
 
Consider causes and possible interventions
 
Repeat assessment within 24-48h if possible
 
Consider drug interruption or discontinuation unless other causes are diagnosed and corrected
 
Consider patient hospitalization and specialized treatment
 

New onset dipstick proteinuria ≥ 3+ OR Protein-creatinine ratio (PCR) ≥ 1g/g Cr (or mg/mmol equivalent as converted by the measuring laboratory)	
 
Consider causes and possible interventions
 
Assess serum albumin & serum total protein
 
Repeat assessment to confirm
 
Consider drug interruption or discontinuation unless other causes are diagnosed and corrected
 

New onset hematuria ≥ 3+ on urine dipstick	
 
Repeat assessment to confirm
 
Distinguish hemoglobinuria from hematuria
 
Urine sediment microscopy
 
Assess sCr
 
Exclude infection, trauma, bleeding from the distal urinary tract/bladder, menstruation
 
Consider bleeding disorder
 

* Corresponds to KDIGO criteria for Acute Kidney Injury	

Additional specialized assessments are available to assess renal function or renal pathology. (Note: In exceptional cases, when a nephrologist considers a renal biopsy, it is recommended to make slide specimen available for evaluation by the RSG to potentially identify project-wide patterns of nephrotoxicity.)

Whenever a renal event is identified, a detailed patient history and examination are indicated to identify and potentially eliminate risk factors that may have initiated or contributed to the event:

- Blood pressure assessment (after 5-minute rest, with an appropriate cuff size)
- Signs and symptoms like fever, headache, shortness of breath, back or abdominal pain, dysuria or hematuria, dependent or periorbital edema
- Changes in blood pressure, body weight, fluid intake, voiding pattern, or urine output
- Concomitant events or procedures such as trauma, surgical procedures, cardiac or hepatic failure, contrast media or other known nephrotoxin administration, or other diseases or causes, e.g., dehydration due to delirium, tumor lysis

**Table 16-5 Renal Event follow-up**

FOLLOW-UP OF RENAL EVENTS

• Urine dipstick and sediment microscopy evidence of DIN: crystals, red blood cells (dysmorphic/glomerular vs. non-dysmorphic/non-glomerular), white blood cells, tubular epithelial cells

• Blood pressure and body weight

• sCr, BUN, electrolytes (sodium, potassium, phosphate, calcium), bicarbonate and uric acid

• Urine output

Review and record possible contributing factors to the renal event (co-medications, other co-morbid conditions) and additional diagnostic procedures (MRI etc.) in the CRF

• Event resolution: (sCr within 10% of baseline or PCR < 1 g/g Cr, or ACR <300 mg/g Cr) or

• Event stabilization: sCr level with <math>\pm 10\%</math> variability over last 6 months or protein-creatinine ratio stabilization at a new level with <math>\pm 50\%</math> variability over last 6 months.

• Analysis of urine markers in samples collected over the course of the DIN event

## **16.4 Appendix 4: Signs/symptoms of severe/complicated malaria**

[figure not shown]
### **Danger signs:**

1. not able to drink or breast feed
2. vomiting > twice within preceding 24 hours
3. one convulsion within preceding 24 hours
4. unconscious state
5. unable to sit or stand

### **Signs of severe malaria:**

Outline bedside clinical classification of severe malaria in children (<12 years) in a high transmission area

Severe falciparum malaria is defined as one or more of the following, occurring in the absence of an identified alternative cause and in the presence of *P. falciparum* asexual parasitemia:

### **Group 1**

[figure not shown]
- Prostrate children (prostration is the inability to sit upright in a child normally able to do so or to drink in the case of children too young to sit). Three subgroups of increasing severity should be distinguished:
  - Prostrate but fully conscious
  - Prostrate with impaired consciousness but not in deep coma
  - Coma (the inability to localise a painful stimulus)
- Respiratory distress (acidotic breathing):
  - Mild – sustained nasal flaring and/or mild intercostal indrawing (recession)
  - Severe – the presence of either marked indrawing (recession) of the bony structure of the lower chest wall or deep (acidotic) breathing
- Shock compensated or decompensated

### **Group 2**

- Children who, although able to be treated with oral antimalarials, require supervised management because of the risk of clinical deterioration but who show none of the features of group 1 (above). These include children with any of the following:
  - Haemoglobin <5 g/dl or haematocrit < 15%
  - 2 or more convulsions within a 24-h period
  - Haemoglobinuria (blackwater)
  - Jaundice

### **Group 3**

Children who require parenteral treatment because of persistent vomiting but who lack any specific clinical or laboratory features of groups 1 or 2 (above).

## 16.5 Appendix 5: Cardiac Alert Threshold Values and Actions

**Table 16-6 Cardiac alert threshold values and actions**

	Values	Actions
QTcF	
 
• QTcF > 500.
 
	
 
• If confirmed by two repeat ECG, check and correct the patient's serum potassium and magnesium immediately.
 

Cardiac rhythm	
 
• Sustained ventricular tachycardia lasting 30 sec or more, or ventricular fibrillation, or any hemodynamically compromising cardiac arrhythmia
 
	
 
• Report as SAE to Sponsor and transmit to central vendor immediately for prompt review.
 
• Discontinue patient from study therapy.
 
• Monitor ECG hourly until at least 2 consecutive hourly ECGs performed are back to baseline
 

QTcF	
 
• Increase from baseline <math>\geq 60</math> ms
 
	
 
• If confirmed by two repeat ECG, check and correct the patient's serum potassium and magnesium immediately.
 

Resting heart rate	
 
• HR < 50/min with > 25% decrease from pretreatment baseline verified by ECG
 
	
 
• Report to Sponsor as AE (unless it meets the SAE criteria as described in Section 10.1.2) and transmit to central vendor immediately for prompt review.
 

27-12-2021	Protocol amendment	This SAP amendment is due to major amendment in protocol including change in objectives design, active comparator etc.	Title change Study design is updated Study objectives and endpoints are updated Pooling strategies are further defined. Study treatment, Study Day, PCR-corrected ACPR are clarified.  Treatment dispositions and compliance related analysis is simplified Primary endpoint analysis is changed Analysis of secondary endpoint is changed Sample size section is modified	Section 1.1 Section 1.2 Section 2.1 Section 2.2.1, 2.13 Section 2.4.1 Section 2.5 Section 2.7.2 Section 3
18-01-2022		Non-compliance with food to be excluded from PPS and PK set Impute missing concomitant medication date same as imputation of missing AE date	PD criteria for OTH04 is updated in Table 5-10 Delete imputation details for concomitant medication date	Section 5.8 Section 5.1.3

Date	Time point	Reason for update	Outcome for update	Section and title impacted (Current)
09-10-2022		Address comments from the Novartis team and Medicines for Malaria Venture:	
Stated the confidence interval level for individual cohorts if constructed. In the primary objective analysis, stated Cohort 2 to be analyzed mainly using descriptive statistics if Cohort 2 stops early;
 
Added additional analysis for FCT by excluding patients who took anti-pyretic drugs prior to FCT;
 
Added a note that patients who take non-study anti-malarial medication due to repeated vomiting of study medication should be considered as treatment failure
 
Added a bullet to consider a patient as PCR corrected responder at Day X if the patient is not classified as a non-responder at Day X and the patient has a malaria blood film showing new infection at Day X using PCR genotyping or later if Day X is missing and another bullet to indicate that new infection at a visit causes PCR-corrected ACPR status unknown in later visits
 
Revised the Per Protocol set (PPS) to exclude new infections before Day 29
	
Sections 2.1, 2.5, and 2.7.2;
 
Sections 2.5.4 and 2.7.2
 
Section 2.1.1.2
 
Sections 2.2 and 5.8

Date	Time point	Reason for update	Outcome for update	Section and title impacted (Current)
24-06-2024		Address comments after the dry run for CSR	Revised the analysis visit window for Day 29 in Table 5-6.	Section 5.1.4
			Added Table 5.13 to describe derivation Criteria of uncorrected ACPR and PCR- corrected ACPR and the sensitive analyses;	Section 5.7.4
			Changed the time to event/censoring from Day 41 to Day 43 in tail of KM plots	Section 2.1.1
			In the definition of uncorrected ACPR, deleted 'new infection' in the last bullet point; In the definition of PCR-corrected ACPR, added 'new infection' at the definition '□The patient is not classified as a non-responder at Day X and the malaria blood film result at Day X is missing and not followed by a subsequent negative result/new infection'.	Section 2.1.1.2
			In the definition of corrected ACPR and uncorrected ACPR, add a patient who take non-study antimalaria medications during the treatment period is considered as non-responder .	
			In the definition of corrected ACPR, add that if the patient has parasite cleared by Day 7 but has negative PCR prior	

Date	Time point	Reason for update	Outcome for update	Section and title impacted (Current)
			to Day X, the response is considered as missing/undetermined.	
			In PK analysis set, added two PK analysis subsets with different food compliance conditions for run-in cohorts and cohort 1 and cohort 2	Section 2.2
			For PCT and FCT censoring, added 'If the study medication is vomited in the same date as the use of antimalarial medication, the last vomiting time on the study medication date is imputed as time of antimalarial medication. Otherwise, the antimalarial medication time can be imputed using the middle day time (12:00).'	Section 2.7.2.4
			Changed the condition of clearance of initial infection from Day 15 to Day 7.	Section 2.7.2.5
			Included cohort 1 and cohort 2 separately for the treatment difference evaluation using a log-rank test	Section 2.7.2
			Changed the condition of clearance of initial infection from Day 15 to Day 7.	Section 2.7.2.6
			Added "Change from baseline will only be analyzed for Hemoglobin, RBC, platelets, TBIL, ALT, AST."	Section 2.8.2

Date	Time point	Reason for update	Outcome for update	Section and title impacted (Current)
			For Post treatment QTcF/QTcB increase from baseline for cohort 1 and cohort 2, it will only be analyzed at common post-baseline timepoints (48H, Day 8, and Day 43)	Section 2.8.3
			Lower limit of the Day 29 visit is changed from Day 25 to Day 27	Section 5.1.4
			In Table 5-6, Added three more time points 51 h, 54h, 68 h for ECG and PK sampling	Section 5.1.4
			Added more prohibited medications, in particular related to Liver enzymes (ALT/AST) elevation and QTc prolongation	Section 5.3

LCF	Late clinical failure
L.O.S.	Level of significance
LPF	Late parasitological failure
MedDRA	Medical Dictionary for Drug Regulatory Affairs
NCI	National Cancer Institute
o.d.	Once Daily
PK	Pharmacokinetics
PPS	Per-Protocol Set
qd	Qua'que di'e / once a day
SAP	Statistical Analysis Plan
SOC	System Organ Class
TFLs	Tables, Figures, Listings
WHO	World Health Organization

1 Introduction

The purpose of this Statistical Analysis Plan (SAP), is to describe the implementation of the statistical analysis, which is planned in the protocol (Version 01). The study has three age descending cohorts: Run-in, Cohort 1, and Cohort 2. Mock shells for the clinical study report (CSR) will be prepared according to the analysis plan specified in this SAP. Statistical outputs for the CSR will be generated after the final database lock (DBL) according to the mock shells and this SAP. A separate set of mock shells will be prepared and executed for DMCs based on this SAP.

Any data analysis carried out independently by the investigator should be submitted to Novartis before publication or presentation.

All CSR analyses will be carried out by using SAS, Version 9.4 or higher.

1.1 Study design

This will be a multicenter, open-label, randomized parallel-group, non-inferiority study in pediatric population with confirmed uncomplicated *P. falciparum* malaria.

The study has three age descending cohorts; Run-in Cohort, Cohort 1 and Cohort 2.

Run-in Cohort:

Male and female adolescent patients (≥ 12 and < 18 years) with at least 35 kg weight will be enrolled in the Run-in cohort. 24 patients (up to 96 in case of dose/food adaptation) will be dosed starting with KAF156 400 mg and LUM-SDF 240 mg QD (once daily) for 2 days; 12 will be under fasted and 12 under fed conditions, in randomized fashion. In case of dose/food adaptation, the Run-in cohort may be repeated up to thrice with maximum of 96 (24 x 4) patients. Once the dose/dose-regimen is deemed optimal (based on safety and PK data review as available), Cohort 1 will start recruitment.

Cohort 1:

Male and female children with age 2 to < 12 years will be enrolled in Cohort 1. Approximately 140 patients will be enrolled in this cohort in 1:1 ratio between KAF156/LUM-SDF and Coartem® groups. In case of Cohort 2 stops early, 80 more patients are planned to be randomized in Cohort 1 (1:1 ratio between KAF156/LUM-SDF and Coartem®) to achieve the required overall sample size for the Cohort 1 and 2, which is 220.

Cohort 2:

[figure not shown]
Male and female children with age 6 months to < 2 years will be randomized in Cohort 2.

Approximately 80 patients (may stop at 24 or 48 patients if dose not optimal) may be enrolled in this cohort. First 24 patients from the age group of 6 months to < 2 years will be randomized. If the dose is deemed optimal (based on safety, PK and efficacy data review as available), then the remaining 56 patients in the cohort will be randomized so that there are approximately 80 treated patients aged 6 months to < 2 years old. In case results (PK, safety and efficacy data) from the initial 24 patients are non-conclusive, another DMC review may be scheduled after

the first 48 patients of Cohort 2 have been dosed and followed up to Day 15. In case that the dose is not optimal (based on safety, PK and efficacy data review as available), the enrollment for this cohort will be terminated. The 80 patients allocated to Cohort 2 will be re-allocated to Cohort 1.

Overall total sample size in Cohort 1 and Cohort 2 will be ranging from 220 to 268 in case of Cohort 2 early termination after either 24 or 48 patients.

Figure 1-1 Study Design

At screening, within each cohort, eligible patients will be randomized into one of the two treatment groups in 1:1 ratio (fasted and fed patients in the Run-in Cohort; KAF156/LUM-SDF and Coartem® in Cohorts 1 and 2)

Randomization is stratified according to [Table 1-1](#) to achieve the balanced treatment allocation within /age group/a country.

Table 1-1 Stratified randomization scheme

Cohort	Stratification factor
Run-in cohort	Country
Cohort 1	Age group (6 to <12 years and 2 to <6 years) and Country
Cohort 2	Country

Patients will be admitted to the hospital on Day 1. They will be dosed according to predefined dosing regimen and will remain in the hospital under close supervision until they are discharged

by the investigator or designee on Day 4. At the discretion of the investigator, patients may stay additional days if needed. The patients will then be followed up at Days 5, 8, 15, 29 (primary analysis time point), and 43. Visits to assess safety and efficacy will be scheduled during the follow-up period as described in the schedule of assessments tables ([Table 8-1](#), [Table 8-2](#), [Table 8-3](#)) in the protocol. If malaria symptoms re-emerge outside the scheduled study visits, patients will be instructed to contact the investigator.

1.2 Study objectives and endpoints

The study objective and end points are included in below table.

Table 1-2 Objectives and related endpoints

Objective(s)	Endpoint(s)
Primary objective(s)	Endpoint(s) for primary objective(s)

 To evaluate the efficacy of KAF156 combined with LUM-SDF compared to Coartem® (non-inferiority trial) for the treatment of uncomplicated malaria caused by P. falciparum in children 6 months to <12 years. 	
 PCR-corrected adequate clinical and parasitological response (ACPR) at Day 29 (i.e., 28 days post-dose) (Cohorts 1 and 2 pooled).
Secondary objective(s)	Endpoint(s) for secondary objective(s)

 To investigate the effect of food on lumefantrine bioavailability in patients 12 to <18 years old (Run-in Cohort). To investigate the effect of food on KAF156 bioavailability in patients 12 to <18 years old (Run-in Cohort). To evaluate safety and tolerability of KAF156/LUM-SDF in pediatric patients (6 months to <18 years old). To assess PK of KAF156 and lumefantrine in pediatric patients (6 months to <12 years old). To further evaluate the efficacy of KAF156 combined with LUM-SDF by assessing uncorrected and corrected ACPR at different time points as well as fever- and parasite-clearance times. 	
 LUM PK parameters such as AUC, Tmax and Cmax (Run-in Cohort). KAF156 PK parameters such as AUC, Tmax and Cmax (Run-in Cohorts). Standard safety/tolerability assessments: AE/SAE incidence and severity, laboratory abnormalities and electrocardiogram (ECG) abnormalities. KAF156 and lumefantrine: PK parameters such as AUC, Cmax (LUM Cmax for Cohorts 1 and 2) C168 h and Tmax. PCR-corrected adequate clinical and parasitological response (ACPR) at Day 15, Day 29 (Run-in Cohort) and Day 43, and the uncorrected ACPR at Day 15, Day 29, and Day 43. Incidence rate of recrudescence and new infection (i.e., reinfection) at Days 15, 29 and 43. Parasite and fever clearance times (PCT and FCT).

Objective(s)	Endpoint(s)

2 Statistical methods

2.1 Data analysis general information

Data will be analyzed by Novartis using SAS version 9.4 according to the data analysis presented in section 12 of the study protocol, which is also available in [Appendix 16.1.1 of the CSR](#). Detailed information is given in the following sections.

Data analyses required for the study Data Monitoring Committee (DMC) will be analyzed by Novartis (Trial statistician/trial programmer for Run-in Cohort and independent statistician/independent programming team for Cohort 1 and 2). The outline of the DMC analysis outputs is presented in the DMC charter and will be detailed in a separate mock shell based on this SAP.

Information on visit windowing, imputation rules and the methods of efficacy and safety analyses is given in the sections to follow. This SAP covers the methods for: DMC meetings, planned interim assessment, and the final analysis.

Unless otherwise stated, summary tables/figures/listings will be on all patients included in the population under consideration.

Categorical data will be presented as frequencies and percentages. For continuous data, n, mean, standard deviation, median, 25th and 75th percentiles (for selected parameters), minimum, and maximum will be presented. Additionally, geometric mean will be presented for PK parameters which may be better described using the lognormal distribution.

Unless otherwise stated, p-values (if required) will be provided for two-sided alternative hypotheses and presented up to 4 significant digits after decimal place; confidence intervals will be presented up to 2 significant digits after decimal place. PK summaries will be presented up to 3 significant digits except CV% , which will be rounded up to 1 digit after decimal.

The dose level/regimen of treatment groups in the run-in cohort may be adjusted after the first 24 patients in the cohort have been dosed. Once it has been adjusted, it becomes a different treatment group. The treatment group will be labeled to include both the full dose level of the study drugs, duration of treatment (no. of doses such as QDx2) and food intake designation (See Section 2.1.1). Cohort 1 and Cohort 2 will be pooled together for the analysis if dose regimen is considered to be similar and Cohort 2 does not stop early. In case of Cohort 2 stops early, Cohort 1 will be recruited with more patients to match the required sample size and hence Cohort 1 will be analyzed separately from Cohort 2; in this situation, Cohort 2 will be analyzed mainly using descriptive statistics. Selected efficacy and safety endpoints will be analyzed on

Cohort 1 and Cohort 2 pooled together. If at least one dose regimen is considered similar among the 3 cohorts, data will be summarized by treatment group for all 3 cohorts pooled in addition to summary by cohort and treatment group. In that case, statistical analysis will in general include a pooled cohort in addition to each cohort.

If Cohort 2 does not stop early, confidence level for comparison with Coartem (if provided) will be based on the 95% level for Cohorts 1 and 2 pooled and the 95% level for individual cohort. If Cohort 2 stops early, confidence level for comparison with Coartem (if provided) will be based on the 95% level for Cohort 1 and the 95% level for Cohort 2.

Note: similar doses among different cohorts are based on the equivalent adult dose according to the current planned weight range (see [Table 6-4](#) in the protocol). However, they may be reassessed based on PK exposures at the end of study.

All post-text tables will be generated using Microsoft Word cell-based format so that they can be easily cut and pasted to create intext tables for the CSR. For the run-in cohort, some treatment groups may consist of doses that are not optimal. All such treatment groups will also be displayed in the post-text tables along with the ones that are the optimal. However, only those treatment groups containing the optimal dose for the run-in cohort are important for displaying in the intext tables. Therefore, post-text tables will display all cohorts including the pooled cohort (if applicable) and all treatment groups under a cohort side by side as columns. Within each cohort, the 2 treatment groups will be displayed side by side.

Although randomization is stratified using country and age category per [Table 1-1](#) statistical analysis will not be stratified accordingly due to small sample sizes in each country/age category. For pooled analyses, study cohort will be used as stratum.

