2.5 Analysis related to the primary objective

The primary objective is to demonstrate the non-inferiority (NI) of a KAF156 and LUM-SDF combination to Coartem[®] for treatment of uncomplicated malaria caused by *P. falciparum* in children 6 months to < 12 years old. The NI margin (Δ) has been set to 10%.

Patients from Cohorts 1 and 2 will be pooled together. In case that Cohort 2 stops early, such as after the first 24 patients, the study objectives will be assessed based on Cohort 1 data alone since there will be enough statistical power for Cohort 1 alone (refer to Section 3.1.1) while Cohort 2 will be analyzed mainly using descriptive statistics.

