3.1.1 Primary endpoint(s)

The primary objective is to evaluate the efficacy of KAF156 combined with LUM-SDF by demonstrating non-inferiority to Coartem[®] in PCR corrected ACPR at Day 29 for treatment of uncomplicated malaria caused by *P. falciparum* in children 6 months to < 12 years old. The NI margin (Δ) has been set to 10%. There is no historical Coartem[®] trial that compared Coartem[®] with placebo in PCR corrected ACPR at Day 29 to justify the NI margin statistically. The 10% NI margin in PCR corrected ACPR at Day 29 is based on clinical judgement as a NI margin of 10% to 12.5% is commonly used in other infection diseases (e.g., FDA 2018 guidance for

Complicated Urinary Tract Infections, FDA 2020 guidance for Hospital-Acquired Bacterial Pneumonia and Ventilator-Associated Bacterial Pneumonia, EMA 2014 Addendum to the guideline on the evaluation of medicinal products indicated for treatment of bacterial infections, etc.).

The statistical null hypothesis is that the difference in PCR-corrected ACPR rate at Day 29 between KAF156 and LUM-SDF combination and Coartem[®] is at most -10% with the alternative hypothesis that it is greater than -10%. The non-inferiority of KAF156 and LUM-SDF combination in PCR corrected ACPR rate at Day 29 will be evaluated based on the per-protocol analysis set using Cohorts 1 and 2 pooled if Cohort 2 does not stop early or using Cohort 1 data alone if Cohort 2 stops early.

Cohort 2 does not stop early

The statistical hypothesis will be evaluated using the lower limit of 2-sided 95% confidence interval (CI) for the difference between two treatment groups using Cohorts 1 and 2 pooled based on Mantel-Haenszel estimate of the common risk difference stratified by cohort (see [SAS manual version 13.2 Pages 2681-2682, 2014](#)). If the lower confidence limit is greater than -10%, the null hypothesis will be rejected. That means the non-inferiority will be established at -10%.

[figure not shown]
Assuming that the true response rate in PCR corrected ACPR at Day 29 is 95% for both treatment groups, a sample size of 92 patients per group will have at least 87% power to reject the null hypothesis that the response rate for KAF156 and LUM-SDF combination is at least 10% lower than Coartem[®] at 1-sided alpha of 2.5% (nQuery 8.4 module PTE0-1/Two Group Test of non-inferiority in Proportions).

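### SAP 2.1 makes pooling of Cohorts 1 and 2 depend on a dose-similarity judgement that may be revisited from end-of-study PK, in conflict with the single early-stop switch used everywhere else for the primary test

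*SAP*

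**What the plan says.** **Pooling in SAP 2.1.** The general section sets two conditions: "Cohort 1 and Cohort 2 will be pooled together for the analysis if dose regimen is considered to be similar", and Cohort 2 must not stop early. A note in the same section bases dose similarity on the equivalent adult dose by weight range, citing protocol Table 6-4, and then adds: "However, they may be reassessed based on PK exposures at the end of study".

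**Pooling elsewhere.** SAP 2.5 says of the primary objective: "Patients from Cohorts 1 and 2 will be pooled together". Its only exception is early stopping of Cohort 2, when Cohort 1 is tested alone. SAP 2.5.2 and 3.1.1 use the same single switch, as do protocol section 12 (opening text), 12.4.1, 12.4.2 and 12.8.1. SAP section 4 lists no changes to the protocol's analyses.

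**Strata.** Cohort 1 is randomised by "Age group (6 to <12 years and 2 to <6 years) and Country" (SAP 1.1, Table 1-1). SAP 2.1 says that "statistical analysis will not be stratified accordingly due to small sample sizes in each country/age category" and keeps cohort as the stratum in pooled analyses.

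**Design figures (SAP 3.1.1).** The margin "has been set to 10" percentage points, tested at "1-sided alpha of 2.5" percent, assuming "the true response rate in PCR corrected ACPR at Day 29 is 95% for both treatment groups". With 92 evaluable patients per arm the stated power is at least 87%. Allowing for 16% exclusion from the per-protocol set gives 220 randomised: about 140 in Cohort 1 and 80 in Cohort 2.

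**The concern.** Which patients enter the primary test should be settled before results are known. SAP 2.1 adds a condition that the protocol lacks and leaves it open until the end of the study, without saying who decides, by what rule, or whether before unblinding.

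The trigger is not independent of the outcome. SAP 3.1.2 makes the 168-hour lumefantrine concentration the key PK check in Cohort 2 because low values go with recrudescence under Coartem, and SAP 2.10 plots Day 8 concentrations by cure status. Infants with low exposure may therefore also be infants with more failures.

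The plan also has a gap. The Cohort 1 test by the Wilson uncorrected method is specified only for the case where Cohort 2 stops early, which is also when Cohort 1 gains 80 patients. Nothing covers a completed Cohort 2 that is judged not similar.

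**Working it through.** **1. Can the condition bind?** Both cohorts receive the dose and regimen selected after the Run-in Cohort (protocol summary), scaled by one weight-band table (protocol 6.1.3, Table 6-3). Protocol 6.5 and 6.5.1 allow dose adjustment only after review of the Run-in Cohort. Protocol section 3 terminates Cohort 2 if its dose is not optimal, which is already the early-stop branch. (Protocol Table 4-1 says in general terms that a data review may trigger a dose change, but 6.5 and 6.5.1 do not carry this into Cohort 2.) On planned dose, then, the cohorts are similar by design, and only the end-of-study PK reassessment could make a completed Cohort 2 not similar.

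**2. Reproduce the stated power.** Unpooled normal approximation, 95% in both arms, margin 0.10, z = 1.96:
- n = 92 per arm: SE = sqrt(2 x 0.95 x 0.05 / 92) = 0.0321; 0.10 / 0.0321 = 3.112; 3.112 - 1.960 = 1.152; power 87.5%. This agrees with the plan.
- 92 / 0.84 = 109.5, so 110 per arm and 220 in total. This also agrees.

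**3. Power if Cohort 2 completes but is not pooled.** Assume 16% exclusion in each cohort.
- Cohort 1: 140 x 0.84 / 2 = 58.8, about 59 per arm. Cohort 2: 80 x 0.84 / 2 = 33.6, taken as 33, so that 59 + 33 = 92.
- Normal approximation, n = 59: SE = 0.0401; 0.10 / 0.0401 = 2.492; 2.492 - 1.960 = 0.532; power 70%.
- Exact enumeration with the SAP's Wilson uncorrected (Newcombe) interval: 59%.

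The two methods differ even at full size: at 92 per arm the Newcombe interval gives 79%. Like for like, the loss is from 87.5% to 70%, or from 79% to 59%.

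**4. Worst-case error.** Suppose non-inferiority could be claimed if either the pooled test (Mantel-Haenszel by cohort, Sato variance) or the Cohort 1 Newcombe test succeeds. Exact enumeration, 59 + 33 per arm, 95% under control:

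| True difference, Cohort 1 / Cohort 2 | Pooled alone | Cohort 1 alone | Either |
|---|---|---|---|
| -10 / -10 points | 3.35% | 2.2% | 4.4% |
| -4.4 / -20 points | 3.1% | 17.6% | 18.2% |

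For the second row the weighted true difference is (59 x -4.4 + 33 x -20) / 92 = -10.0 points. The large-sample counterpart of the first row, with correlation sqrt(58.8 / 92.4) = 0.80, is a rise from 2.5% to 3.9%.

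**5. Age strata.** Simulated power of the pooled test, with Cohort 1 split 29/30 per arm by age group and 33 per arm in Cohort 2. The age gradients are assumptions; the documents give none.

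| Response in the two Cohort 1 age groups (Cohort 2 at 95%) | By cohort | By cohort and age group |
|---|---|---|
| 95% / 95% | 86.1% | 86.1% |
| 92% / 98% | 86.4% | 86.7% |
| 90% / 99% | 85.0% | 85.9% |

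One-sided error at the margin is 3.3% to 3.4% either way.

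**The case against.** The strongest reply is that every section governing the primary test has the one switch, and SAP section 4 disclaims any change. The SAP 2.1 sentence is general text, and its note follows a passage on summaries across all three cohorts, so it may have been meant only for those. The trial team is blinded in Cohorts 1 and 2 (protocol 6.4), the trigger is PK and not response, and SAP 2.7.2.1 plans intervals for each cohort, so a poor infant result would still be visible. All of this stands. It makes the defect a conflict to resolve. It does not remove it, because the SAP 2.1 condition is worded for pooling Cohorts 1 and 2 and no text limits the reassessment to exploratory use or to a time before unblinding.

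Three stronger readings are tempting, and the documents do not support them.

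- *The SAP plainly licenses re-choosing the primary population after the results.* It does not: SAP 2.5, 2.5.2 and 3.1.1 say otherwise.
- *The false-positive risk is 18%.* That figure assumes a free choice of test. Of the 18.2%, 17.6% is success of the Cohort 1 test when Cohort 1 is truly within the margin. That conclusion is correct for ages 2 to under 12 years and false only if extended to infants.
- *The SAP removes an age stratification that the protocol required.* Protocol 12.4.2 already specifies stratification by cohort only, and no stratification for Cohort 1 alone. Cohort is itself an age split, and SAP 2.7.2.7 summarises response by age group.

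The citation of protocol Table 6-4 is wrong, since that is the Coartem table, but its weight bands match those of Table 6-3, so nothing numerical follows from it.

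**Conclusion.** The point holds as an unresolved conflict about the primary test population. SAP 2.1 adds a pooling condition that can bind only through a late, undefined PK judgement. The protocol and the SAP's own primary-analysis sections have no such condition, and the branch it opens has no specified analysis. In that branch power would be about 59% to 70%, depending on method, against the stated 87%. The worst-case inflation of one-sided error is about one percentage point (3.35% to 4.4%) when both cohorts lie at the margin. This is an upper bound, since PK and not response is the trigger.

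These figures assume 16% exclusion in each cohort and 95% response under control. It should be corrected before database lock. The age-strata point is minor: about 1 power point or less under assumed gradients, with no effect on error. The reason given, small country-by-age cells, does not apply to two age groups sharing at least 140 patients, but this does not call for a change to the primary method.

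**What to change.** - In SAP 2.1, state that for the primary objective Cohorts 1 and 2 are pooled unless Cohort 2 was stopped early through the DMC process. This matches SAP 2.5, 2.5.2 and 3.1.1 and the protocol, and it closes the branch with no specified analysis.
- Limit PK-based reassessment of dose similarity to exploratory or three-cohort summaries, and say so in the note.
- Correct the table reference in the note from protocol Table 6-4 to Table 6-3.
- Optionally, add a supportive Mantel-Haenszel analysis of ACPR by three age groups (6 months to under 2, 2 to under 6, 6 to under 12 years). Keep the protocol's primary methods as they are. In particular, do not put a stratified interval in place of the Wilson uncorrected interval if Cohort 1 is tested alone.

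The first three are wording changes to one SAP section. The fourth costs one more programmed output. None affects sample size, conduct or the protocol.
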